## 6. STUDY POPULATION AND SUBJECT SELECTION CRITERIA

The study population consists of patients affected by neurodegenerative diseases, referred to IRCCS Ospedale Policlinico San Martino (Genoa), Fondazione IRCCS Cà Granda Ospedale Maggiore Policlinico (Milan), and any additional Units that may join the study following Ethics Committee (EC) approval. Eligible subjects will be identified during outpatient visits conducted as part of routine clinical follow-up at the participating centers. At these visits, patients will be invited to participate in the study.

The clinical diagnosis will be established according to the criteria detailed below.

### Eligibility Criteria

Subjects will be enrolled only if they fulfill all inclusion criteria and none of the exclusion criteria for each neurodegenerative condition under investigation, as described below.

#### ALZHEIMER'S DISEASE (AD)

##### Inclusion criteria

- Signed written informed consent from the patient and/or legal representative (Appendix X);
- Age  $\geq 18$  years;
- Clinical diagnosis of AD in patients referred to the participating clinical centers, as follows:
  - Predominantly amnestic presentation based on primary complaint and comprehensive neuropsychological assessment;
  - MMSE  $>24$ , with instrumental activities of daily living preserved (MCI) or mildly impaired (mild dementia), corresponding to a CDR score of 0.5 and 1, respectively;
  - Absence of significant neurological/systemic comorbidities or structural abnormalities indicative of other causes of cognitive impairment on morphological imaging;
  - Absence of non-AD-related structural abnormalities on imaging review;
  - CSF biomarkers (A $\beta$ 42, A $\beta$ 40, p-Tau181, t-Tau) consistent with AD profile (A+T+) or amyloid-positive PET with fluorinated tracers, according to current diagnostic criteria for AD-related MCI and dementia;
  - Availability of longitudinal clinical assessments, including MMSE and daily living activities, for at least 24 months.

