##### Exclusion criteria

- Failure to meet any of the above inclusion criteria.

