**PARKINSON'S DISEASE (PD)**

**Inclusion criteria**

- Signed written informed consent from the patient and/or legal representative (Appendix X);
- Age  $\geq 18$  years;
- Clinical diagnosis of PD according to revised MDS criteria, as follows:

- Predominant motor presentation with bradykinesia plus resting tremor and/or rigidity;
- MMSE  $>24$ , with preserved (MCI) or mildly impaired (mild dementia) instrumental daily living activities (CDR 0.5–1);
- Absence of significant neurological/systemic comorbidities or structural abnormalities indicative of other causes of cognitive impairment;
- Imaging findings:
  - a) Normal structural brain imaging;
  - b) Striatal DAT binding reduction on SPECT DAT-SCAN;
- Availability of longitudinal clinical assessments, including motor scales (e.g., UPDRS-III, Hoehn & Yahr), MMSE/MOCA, and daily living activities, for at least 24 months.

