#### - Baseline visit and informed consent

The Investigator will invite patients to participate after verifying inclusion/exclusion criteria. Patients (or legal representatives in case of cognitive impairment) will receive detailed information on study aims, benefits, and potential risks, along with written information sheets and informed consent forms. Adequate time will be allowed for discussion with the general practitioner before consent. Patients will also be asked whether they agree to be re-contacted for future research studies.

Investigators at the Genoa and Milan centers are responsible for obtaining and archiving signed informed consent before any study-specific procedures.

#### - Visit 1

At this visit, informed consent will be obtained, and subjects will be enrolled with assignment of a pseudonymized code generated in REDCap using the Mainzelliste algorithm (PMID: 25656224). The algorithm processes identifying attributes (e.g., name, surname, date of birth) to generate a unique, anonymous personal identifier (PID), ensuring record linkage across multiple databases while tolerating spelling variations.

Peripheral blood (20–25 mL) will be collected for preparation of PBMCs, serum, and/or plasma, and urine will be collected for omics analyses. DNA will be extracted from whole blood, RNA preferably from PBMCs; saliva may be used as an alternative genetic source. Sampling will be integrated into routine clinical workflow.

Clinical and biological data will be collected at IRCCS Policlinico San Martino ([name]), Fondazione IRCCS Cà Granda ([name] [name]), and other participating centers.

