### Statistical Approaches

Descriptive statistics will be generated to report the percentage of variants relative to the total enrolled cohort and to the control populations (European and Italian), stratified by disease (PD, parkinsonism, AD, FTD, YOD, ALS, and MCI), individual genes, and specific mutations.

Molecular–genetic data (single variants or variant groups) and clinicopathological data (diagnosis, disease stage, prognostic/predictive parameters, survival) will be analyzed using both numerical and graphical approaches. Frequency and contingency tables will be constructed, and statistical indices (means, percentiles, standard deviation) will be computed. Data will be visualized through histograms, boxplots, and scatterplots. Appropriate statistical tests—including t-tests, Fisher's exact test, and others depending on the formulated hypotheses—will be applied. Enrolled patients will be monitored through active follow-up as part of routine diagnostic care. Data regarding disability progression, disease course, and overall survival will be analyzed by diagnosis, mutation, or mutation combinations, as well as treatment received, using Kaplan–Meier survival analysis.

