### Screening Failure

If it is determined that a subject is not eligible for enrollment despite having provided informed consent (e.g., due to an incorrect diagnosis), the patient will be classified as a screening failure. In such cases, all collected data will be deleted and any biological samples destroyed.

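### A binding 24-month assessment requirement for AD, FTLD, DLB and PD, with no stated direction in time, tilts the cohort toward longer-surviving, retained patients before progression and survival are analysed

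*Protocol*

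**What the plan says.** The AD, FTLD and DLB inclusion lists in Protocol section 6 each require "Availability of longitudinal clinical assessments, including MMSE and daily living activities, for at least 24 months". The PD list requires "Availability of longitudinal clinical assessments, including motor scales (e.g., UPDRS-III, Hoehn & Yahr), MMSE/MOCA, and daily living activities, for at least 24 months". The MCI and ALS lists contain no equivalent.

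The item is binding. Under Eligibility Criteria, "Subjects will be enrolled only if they fulfill all inclusion criteria and none of the exclusion criteria", and the only exclusion criterion in each disease list is "Failure to meet any of the above inclusion criteria". Section 6 also says how patients are found: "Eligible subjects will be identified during outpatient visits conducted as part of routine clinical follow-up at the participating centers". Section 7.1 sets the order of events: "The Investigator will invite patients to participate after verifying inclusion/exclusion criteria".

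The same four lists require MMSE above 24 and CDR 0.5 to 1, without saying at what date these are judged.

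On analysis, section 7.4 (Statistical Approaches) states that "Data regarding disability progression, disease course, and overall survival will be analyzed by diagnosis, mutation, or mutation combinations", and also by treatment received, with Kaplan-Meier as the method. Primary objective 5 in section 5 concerns the impact of molecular mechanisms on disease progression. The PD text after the secondary objectives compares rapid with slow progressors at 5 years.

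**The concern.** Entry is tied to having a stretch of follow-up, and the study then analyses what happens during follow-up. A patient who dies or is lost early may be unable to satisfy the criterion, so the enrolled cohort is healthier and better retained than the patients it is meant to represent.

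The tilt also differs by diagnosis, because two of the six lists lack the rule. Survival or progression curves compared across diagnoses would then reflect different entry conditions as well as different diseases. Within a diagnosis, variants that shorten survival would be under-represented among those enrolled. The item is fixed in the eligibility section, so an analysis plan written later cannot bring back patients who were never enrolled.

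**Working it through.** **1. Share of the cohort under the rule.** Section 7.4 gives PD ~30%, AD ~30% and FTD ~10%. Taking the FTD share as governed by the FTLD list, 30 + 30 + 10 = 70%, or about 700 of 1,000 patients. DLB has no stated share. ALS (~15%) and MCI (~5%) are outside the rule.

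**2. What each reading does.**

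| Reading of the 24 months | Verifiable before invitation (section 7.1)? | Who is selected out |
|---|---|---|
| Existing records before enrolment | Yes | Patients who died or were lost within 24 months of first assessment |
| Follow-up after enrolment | No | Patients who die or stop attending before month 24, if the criterion is enforced |
| Patient expected to be available for follow-up | Yes | No one on the basis of outcome, but the text does not say this |

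The first two follow the wording, which asks for assessments to be available for at least 24 months. The third needs words that are not there.

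**3. Size of the loss to death.** The protocol gives no mortality figure for AD, FTLD, DLB or PD, and no planned figure to reproduce. With a constant annual hazard h (assumed 0.05 to 0.10), the share dead by 24 months is 1 - exp(-2h):

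- h = 0.05: 1 - exp(-0.10) = 9.5%
- h = 0.10: 1 - exp(-0.20) = 18.1%

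Parametrised by an assumed median survival M in years, the share is 1 - 2^(-2/M): 24.2% for M = 5, 15.9% for M = 8, 12.9% for M = 10 and 8.8% for M = 15.

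**4. Effect on carrier frequency.** Assume 10% carriers and a hazard ratio of 2. The carrier share among 24-month survivors is 0.1·exp(-4h) / [0.1·exp(-4h) + 0.9·exp(-2h)]:

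- h = 0.05: 0.0819 / (0.0819 + 0.8144) = 9.1%
- h = 0.10: 0.0670 / (0.0670 + 0.7369) = 8.3%

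With M from 5 to 15 years, the corresponding range is 7.8% to 9.2%.

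**5. Effect on a survival curve, under one condition.** Suppose the 24 months run from diagnosis, the clock starts at diagnosis and delayed entry is ignored. Apparent 5-year survival is then 2^(-3/M), against a true 2^(-5/M):

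- M = 5: 66% against 50%
- M = 15: 87% against 79%

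That is an overstatement of about 8 to 16 percentage points. It does not arise if the clock starts at enrolment or if delayed entry is handled.

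**The case against.** The strongest reply is that the criterion may only mean that the patient is expected to be available for follow-up. That can be judged at invitation, suits a prospective study that follows routine visits, and keeps early deaths in. It is a possible intention, but it is not what the wording says, and sites could reasonably apply the other readings.

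Several stronger inferences are tempting and are not supported:

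- **That the rule by itself removes fast decliners.** It does not: a patient who declines quickly but survives and is still assessed meets it. Further depletion arises only if MMSE above 24 and CDR 0.5 to 1 also apply at enrolment. Those items sit under the clinical diagnosis and carry no date, so they may describe status at diagnosis. A cap applied at enrolment would also select against decliners without the 24-month rule. I therefore attach no figure to this effect.
- **That 24-month survival is 100% by construction.** That needs a clock starting before enrolment, and the protocol names no time origin. Time origin and delayed entry are commonly left to the SAP, which is not at hand, so their absence is not a finding here.
- **That no newly diagnosed patient can enter.** The item asks for assessments, not assessments since diagnosis, so someone followed through an MCI phase could qualify. The MCI list has no such item.
- **That patients who die early are deleted.** Section 8 (Screening Failure) says of patients found ineligible after consent that "all collected data will be deleted and any biological samples destroyed", but its example is an incorrect diagnosis. No text removes an enrolled patient who later dies or stops attending.

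It is also fair that the main stated goal is variant identification, that survival is covered briefly and without a formal hypothesis, and that the sponsor may want longitudinal data deliberately. This limits the consequences, but a follow-up target would serve that purpose as well.

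**Conclusion.** The point holds as a design weakness. A binding entry item covering about 70% of the planned cohort, and absent for MCI and ALS, has no stated direction in time. On either reading that follows its wording, it favours longer-surviving and retained patients before progression and survival are compared by diagnosis and mutation.

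The direction of the tilt is clear on those readings. Its size is not, because every input is assumed: 5-10% annual mortality gives roughly 10-18% of incident cases dead within 24 months, and a carrier hazard ratio of 2 moves a 10% carrier frequency to roughly 8-9%. The mortality effect on carrier frequency is therefore modest. If the 24 months precede enrolment, a delayed-entry analysis could correct the survival time scale, but it would not recover excluded patients. It could not repair a rule that depends on the future.

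**What to change.** Amend the four inclusion lists and the related text:

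- Replace the 24-month item with a follow-up target. Where slope estimation needs 24 months of data, make it a condition of that analysis set rather than of entry.
- State the date at which MMSE and CDR are judged for eligibility.
- Record the dates of first assessment and of enrolment for every patient.
- Start the survival clock at enrolment, or use delayed entry where earlier assessments are used.
- Keep patients with shorter follow-up in the cohort, as censored or dead.
- Keep patients already enrolled under the rule, with a flag so that a sensitivity analysis can separate them.

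The cost is a protocol amendment to four criteria lines plus a few clarifying sentences, with no added visits or procedures. The downside is that some patients will have short follow-up and contribute little to slope estimates.

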##### Exclusion criteria

- Failure to meet any of the above inclusion criteria.

#### FRONTOTEMPORAL LOBAR DEGENERATION (FTLD)

##### Inclusion criteria

- Signed written informed consent from the patient and/or legal representative (Appendix X);
- Age  $\geq 18$  years;
- Clinical diagnosis of FTLD in patients referred to the participating centers, as follows:

- Predominant behavioral/dysexecutive presentation or progressive language impairment based on primary complaint and full neuropsychological evaluation, according to current diagnostic criteria;
- MMSE >24, with preserved (MCI) or mildly impaired (mild dementia) instrumental daily living activities (CDR score 0.5–1);
- Absence of significant neurological/systemic comorbidities or structural abnormalities indicative of other causes of cognitive impairment;
- Imaging findings consistent with bvFTD [one of the following required]:
  - a) Prominent frontal and/or anterior temporal atrophy on structural imaging;
  - b) Frontal/anterior temporal hypoperfusion or hypometabolism on PET or SPECT;

**OR**

- Imaging consistent with primary progressive aphasia (PPA) [one of the following required]:
  - a) Prominent left posterior fronto-insular/parietal atrophy (non-fluent variant, nfvPPA) or anterior temporal lobe atrophy (semantic variant, svPPA) on structural imaging;
  - b) Hypoperfusion or hypometabolism in the same regions on PET or SPECT;
- Availability of longitudinal clinical assessments, including MMSE and daily living activities, for at least 24 months.

#### **Exclusion criteria**

- Failure to meet any of the above inclusion criteria.

### **DEMENTIA WITH LEWY BODIES (DLB)**

#### **Inclusion criteria**

- Signed written informed consent from the patient and/or legal representative (Appendix X);
- Age ≥18 years;
- Clinical diagnosis of DLB in patients referred to the participating centers, as follows:

- Predominantly non-amnestic cognitive impairment (visuospatial, dysexecutive, attentional) based on patient report or full neuropsychological assessment, plus characteristic clinical features according to current diagnostic criteria for DLB or MCI-LB;
- MMSE >24, with preserved (MCI) or mildly impaired (mild dementia) instrumental daily living activities (CDR 0.5–1);
- Absence of significant neurological/systemic comorbidities or structural abnormalities indicative of other causes of cognitive impairment;
- Supportive instrumental or imaging findings consistent with probable DLB, at least one of:
  - a) Polysomnographic confirmation of REM sleep behavior disorder without atonia;
  - b) Reduced striatal dopamine transporter uptake on SPECT/PET;
  - c) Abnormal cardiac [123I]-MIBG scintigraphy (reduced uptake);
- Availability of longitudinal clinical assessments, including MMSE and daily living activities, for at least 24 months.

#### **Exclusion criteria**

- Failure to meet any of the above inclusion criteria.

### **MILD COGNITIVE IMPAIRMENT (MCI)**

#### **Inclusion criteria**

- Signed written informed consent from the patient and/or legal representative (Appendix X);
- Age ≥18 years;
- Clinical diagnosis of MCI in patients referred to the participating centers, defined as:

- Subjective memory complaint (preferably corroborated by an informant);
- Intact ability to perform daily activities (e.g., meal preparation);
- Preserved general cognitive abilities;
- Objective evidence of memory deficit;
- Absence of dementia.

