correlation between clinical, genetic, and neuropathological features, represents a major challenge to the development of unified pathogenic models and, consequently, effective disease-modifying strategies. The rising prevalence of FTD and its escalating public health impact highlight the critical need for therapies that can prevent the disease, delay its onset, slow its progression, and ease its symptoms.

Other forms of early-onset dementia (**Young Onset Dementia, YOD**), with onset before 65 years of age, have an estimated prevalence of 119 cases per 100,000, corresponding to approximately 3.9 million individuals worldwide. Although AD and FTD are the leading causes of YOD, this group comprises a wider range of disorders. Indeed, YOD can be associated with conditions such as Huntington's disease and vascular dementia, while the accumulation of proteins (e.g., amyloid- $\beta$ ) may give rise to atypical AD variants, such as posterior cortical atrophy or the behavioral/frontal variant. This phenotypic heterogeneity is also observed in genetically determined forms of YOD. Biomarkers—including plasma and cerebrospinal fluid proteins, neuroimaging, and genetic markers—have shown promise for early identification of YOD and for improving understanding of overlapping psychiatric and neurodegenerative symptoms in younger patients. Therefore, clinical management of YOD should consider the specific age-related challenges of younger dementia patients and their families, and provide integrated social, healthcare, and financial support tailored to both age and type of disability.

**Mild Cognitive Impairment (MCI)** represents an intermediate condition between physiological age-related cognitive decline and dementia, characterized by cognitive impairment greater than expected for age, yet with preserved functional independence in daily life. Unlike dementia, autonomy remains intact. The most recent definition of MCI was proposed by Petersen and colleagues.

A major challenge in MCI is the variability of clinical trajectories depending on the underlying etiology. Three main outcomes are possible:

- stability: some individuals with MCI remain stable for extended periods without significant decline ("stable MCI").
- recovery: in certain cases, cognitive function improves and returns to normal or near-normal levels.

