**Exclusion criteria**

- Failure to meet any of the above inclusion criteria.

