**AMYOTROPHIC LATERAL SCLEROSIS (ALS)**

**Inclusion criteria**

- Signed written informed consent from the patient and/or legal representative (Appendix X);
- Age  $\geq 18$  years;
- Clinical diagnosis of motor neuron disease in patients referred to participating centers, as follows:

- Diagnosis of definite or probable ALS according to revised El Escorial criteria;
- EMG must demonstrate:
  - a) Active denervation (fibrillation potentials, positive sharp waves, complex fasciculations);
  - b) Chronic denervation (prolonged, often polyphasic motor unit potentials, reduced recruitment with high firing frequency at maximal effort);
  - c) Nerve conduction studies typically show reduced motor potential amplitude with preserved or minimally reduced motor conduction velocity, normal sensory conduction, and absence of conduction block;
- Transcranial magnetic stimulation (TMS) may demonstrate UMN involvement (reduced corticobulbar/spinal conduction velocity, decreased cortical motor neuron excitability);
- Neuroimaging and laboratory investigations must exclude compressive, infiltrative, or inflammatory conditions mimicking UMN/LMN signs.

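### Of the six eligibility sets in section 6, only the MCI set does not exclude other causes of impairment, so non-neurodegenerative MCI can be enrolled and reported as a case

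*Protocol*

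**What the plan says.** Protocol section 6, under Eligibility Criteria, lets the written lists decide who enters: "Subjects will be enrolled only if they fulfill all inclusion criteria and none of the exclusion criteria for each neurodegenerative condition under investigation". Six lists follow.

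The MCI list begins "Clinical diagnosis of MCI in patients referred to the participating centers, defined as". Apart from consent and age it has five items, of which the only objective one is "Objective evidence of memory deficit". Its single exclusion criterion is "Failure to meet any of the above inclusion criteria".

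The other five lists each address cause:

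- AD: "Absence of significant neurological/systemic comorbidities or structural abnormalities indicative of other causes of cognitive impairment on morphological imaging", plus a CSF or amyloid PET profile.
- FTLD, DLB and PD: "Absence of significant neurological/systemic comorbidities or structural abnormalities indicative of other causes of cognitive impairment", plus supportive imaging or instrumental findings.
- ALS: "Neuroimaging and laboratory investigations must exclude compressive, infiltrative, or inflammatory conditions mimicking UMN/LMN signs".

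Section 3 describes the MCI patients as having a neurodegenerative cognitive disorder at that stage, and the opening of section 6 describes the whole population as patients with neurodegenerative disease. Section 1.1 says that the course of MCI depends on its cause and that "in certain cases, cognitive function improves and returns to normal or near-normal levels". Section 7.4 expects MCI to be about 5% of at least 1,000 patients, counts these among the patients with neurodegenerative disease, and reports MCI as a separate disease stratum.

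**The concern.** The rule that decides enrolment and the statement of who is being studied do not match for MCI. A patient whose memory deficit comes from vascular or systemic disease satisfies all five MCI items, yet lies outside the population in sections 3 and 6.

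The position of the MCI set sharpens this. The AD, FTLD and DLB sets already take patients at the MCI stage (CDR 0.5) when there is evidence for those diseases. The separate MCI set is therefore the natural route for patients with no aetiological evidence, where excluding other causes matters most.

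At stake is the meaning of the MCI results. If some cases have no neurodegenerative disease, their variant frequencies at relevant loci should resemble those of controls, and the odds ratios planned in section 7.4 move toward 1 in that stratum.

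**Working it through.** **Step 1: compare the six lists.**

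| Set | Other causes or mimics excluded? | Supportive imaging, biomarker or neurophysiology required? |
|---|---|---|
| AD | Yes | Yes |
| FTLD | Yes | Yes |
| DLB | Yes | Yes |
| ALS | Yes | Yes |
| PD | Yes | Yes |
| MCI | No | No |

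The count is 1 of 6 without such a clause. Parkinsonism and young-onset dementia appear in the section 7.4 distribution but have no list at all. That is a separate gap, so the statement applies to the lists that are written.

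**Step 2: size of the stratum.** The section 7.4 shares are 30 + 5 + 30 + 10 + 5 + 5 + 15 = 100%. MCI is 5% × 1,000 = 50. Section 7.4 states that the sample size rests on no power calculation, so there is no power figure to reproduce. About 200 internal controls are planned.

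**Step 3: dilution within the stratum.** Let f be the share of enrolled MCI patients without neurodegenerative disease, p1 the carrier frequency in true cases and p0 that in controls. Assume that misclassified patients carry the variant at frequency p0. Then

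observed frequency = (1 − f)·p1 + f·p0, so observed difference = (1 − f)·(p1 − p0).

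With the variance treated as roughly unchanged, the sample needed to detect the difference equally well grows by 1/(1 − f)². The protocol gives no f. The values below are assumptions.

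| f | True cases of 50 | 1/(1 − f)² |
|---|---|---|
| 10% | 45 | 1.23 |
| 20% | 40 | 1.56 |
| 30% | 35 | 2.04 |

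**Step 4: one worked illustration.** Assume p0 = 15%, a true odds ratio of 3.0, 50 MCI patients against 200 controls and two-sided α = 0.05. The case odds are 3 × 0.15/0.85 = 0.529, so p1 = 0.529/1.529 = 0.346.

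| f | Observed frequency | Observed odds ratio | Power |
|---|---|---|---|
| 0 | 0.346 | 3.00 | 85% |
| 10% | 0.327 | 2.75 | 79% |
| 20% | 0.307 | 2.51 | 70% |
| 30% | 0.287 | 2.28 | 61% |

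Other assumed settings behave the same way. With p0 = 25%, an odds ratio of 2.0 falls to 1.76 at f = 20%. With p0 = 5%, an odds ratio of 4.0 falls to 3.33.

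**Step 5: pooled analyses.** Assume the same true difference in every disease group. At f = 10 to 30%, 5 to 15 patients are misclassified.

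- Whole cohort: 0.5 to 1.5% of 1,000, so 1/(0.995)² = 1.01 to 1/(0.985)² = 1.03.
- AD, FTD, young-onset dementia and MCI together (300 + 100 + 50 + 50 = 500): 1 to 3%, so 1/(0.99)² = 1.02 to 1/(0.97)² = 1.06.

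Even at f = 50% the whole-cohort factor is only 1/(0.975)² = 1.05.

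**The case against.** The strongest reply is that the protocol already confines the study to neurodegenerative disease in sections 3 and 6, and that the Screening Failure paragraph in section 8 removes patients with an incorrect diagnosis. This rules out saying that such patients will be enrolled. It does not close the gap. Those statements give intent without a test to apply, and vascular MCI is a correct diagnosis of MCI as section 6 defines it, so it does not clearly count as a screening failure.

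A second reply is that an aetiologically open MCI group may be intended, because MCI with AD, FTLD or Lewy-body evidence has its own route and follow-up can show how the rest evolve. That would be a legitimate design, but the protocol does not declare it and counts these patients as neurodegenerative cases.

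A reader might also infer three larger harms that the document does not support:

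- **A 4-fold sample penalty.** This needs f = 50%. Nothing in the protocol supports that value, and there is no power target to inflate.
- **Material damage to pooled or cross-disorder analyses.** Step 5 puts it at a few per cent.
- **Biomarker differences also pulled toward zero.** That requires misclassified patients to have control-level values. Section 7.3 describes neurofilament light chain as a general marker of neuroaxonal damage, so the bias could go either way.

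**Conclusion.** The inconsistency stands: the MCI list admits patients whom sections 3 and 6 place outside the study population, and it is the only written list that does so for want of a cause-related criterion. The supportable wording is that such patients can be enrolled. The protocol does not show that they will be, or in what number.

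The consequence is confined mainly to a stratum of about 50. For variant frequencies the differences shrink by about (1 − f), equivalent to a 1.2- to 2.0-fold larger sample at an assumed f of 10 to 30%. This rests on two assumptions: the value of f, and control-level carrier frequencies in misclassified patients. A statistical analysis plan could add sensitivity analyses but could not change who was enrolled, so the protocol is the place to settle the point. It is worth correcting because the correction is small, but it does not threaten the study as a whole.

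**What to change.** Reconcile the MCI list in section 6 with section 3 and the opening of section 6, in one of two ways.

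1. **Add the line already used for FTLD, DLB and PD:** "Absence of significant neurological/systemic comorbidities or structural abnormalities indicative of other causes of cognitive impairment". Judge it from the medical history and any neuroimaging findings recorded at Visit 1 (section 7.1). State that no new imaging is required, since nothing in the protocol obliges MCI patients to have it and the AD wording refers to morphological imaging. Where CSF or PET results exist from routine care, record them and report the MCI analyses with and without biomarker-negative patients.
2. **Declare the stratum aetiologically unselected,** if that is the intention, and keep it out of the neurodegenerative case group in pooled analyses.

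The first option costs one eligibility line and some MCI referrals, in a number the protocol does not allow one to estimate. It reduces misclassification but does not remove it. Patients with no visible lesion or relevant comorbidity, including some who later revert to normal cognition, would still enter. The second option costs no recruitment but narrows what the pooled case group contains.
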